## 11.3 Missing Data

Where data is incomplete despite the efforts to ensure continuous high quality data collection and reporting, information relating to the corresponding participant will be excluded from relevant analyses. A dropout rate of 5% has been accounted for in the sample size calculation.

## 11.4 Health Economic Analysis

#### 11.4.1 Clinical Effectiveness Modelling

The clinical effectiveness of a test-based protocol used to stop empirical antifungal therapy will be modelled for each index test & test combination. This will take account of their diagnostic accuracy as well as the expected benefits and disadvantages of using such protocols to stop treatment. Benefit will be based on unnecessary antifungal treatment avoided (expressed as number of treatment-days) and disadvantage based on necessary antifungal treatment inappropriately stopped. This analysis will include estimation of the proportion of patients receiving unnecessary antifungal treatment, which will be derived from the two reference standards used in the main analysis and expressed as a range with 95% CI. We will take account of various degrees of implementation of the proposed protocol to reflect reduced compliance due to factors such as severity of illness and Candida colonisation rates, which may influence clinical practice (even though this may not always be appropriate influence).

#### 11.4.2 Economic Modelling

Given that this is a diagnostic test accuracy study, with participants treated in accordance with standard NHS practice, it is not possible to conduct a cost-effective analysis solely from the results of the trial. As such, all evidence produced on the relative cost-effectiveness of the three tests will need to be modelled. All analyses will be conducted in accordance with the NICE reference case. The most important data required for the analysis is the relative sensitivity and specificity of each strategy (consisting of a single or multiple tests). These data would allow proportions from a hypothetical cohort of patients to be divided into patients who had antifungal treatment appropriately discontinued earlier than occurs with standard care (due to a protocol incorporating an index test), and those patients who had antifungal treatment inappropriately discontinued earlier than occurs with standard care (due to a protocol incorporating an index test). These two groups represent patients who would benefit from the introduction of a protocol incorporating the index tests and those who would be harmed.

The cost and quality adjusted life year (QALY) implications associated with each group would be estimated from modelling. An outline of the anticipated model is provided. A key concept will be the division of the population into four for each index test under study. It is envisaged

Doc No: TM09-LB01 Protocol Version 8.0 Final\_27.05.2021 Page 28 of

that the distribution of patients across the four categories can be estimated from the A-Stop study. The categories are:

- 1) A patient has fungal infection and the index test shows a positive result (true positive)
- 2) A patient has fungal infection and the index test shows a negative result (false negative)
- 3) A patient does not have a fungal infection and the index test shows a positive result (false positive)
- 4) A patient does not have a fungal infection and the index test shows a negative result (true negative)

For all four populations there will be an increase in the costs associated with the use of a new, rapid, test in addition to standard practice. This will be estimated from data collected in the A-Stop study.

Initial clinical advice suggest that where the rapid (index) test is positive (populations 1 and 3) there would be no change in the clinical management of the patient.

[figure not shown]
There would, however, potentially be different clinical management for population 2 (where antifungals may be inappropriately stopped) and for population 4 (where antifungals may be appropriately stopped).

Patients in Population 2 are at increased risk of adverse outcomes (mortality and morbidity) and there may be cost implications, both of reduced drug costs and potentially for longer duration of hospitalisation (both in the ICU and total duration of stay). Patients in Population 4 are not at risk of fungal infection and there may be a reduction in drug costs, and potential reductions in adverse events associated with antifungal treatment and duration of hospitalisation.

A schematic of the anticipated model for patients with a false negative result is provided in Figure 2. Key information denoted in the figure are described below. It is anticipated that these values would be populated from a mixture of literature review, the A-Stop study and elicitation where necessary.

- 1) Alpha and Beta provide the relative survival between those who receive standard care and those who have antifungals withdrawn inappropriately following a rapid test.
- 2) Mu and Sigma provide the relative proportion of survivors who have impaired quality of life dependent on whether they received standard care or had antifungals withdrawn inappropriately following a rapid test. It is possible that there will be multiple impairment states based on the data identified.
- 3) R. This will be dependent on the age of the patient. It is possible that there may be a reduction in utility, but not that associated with impaired states.
- 4) X and M would be calculated taking into account any data on life expectancy and utility (which could differ between treatments). Y and N would be calculated based on life expectancy and cost per year (we may need to elicit this) Separate values have been used for standard of care and the rapid test arms to allow for any difference in the costs and disutility of impairment between the arms.

Doc No: TM09-LB01 Protocol Version 8.0 Final\_27.05.2021 Page 29 of

In addition there will be costs associated with increased drug costs in the standard care arm, and potential differential in utility within the patient treatment phase, and potentially longer duration of hospitalisation.

Figure 2: Anticipated model structure for patients with false-negative index test result.

The model will allow an estimate of the cost per QALY gained to be produced which would allow the cost-effectiveness of the strategies evaluated to be viewed within the context of published NICE cost-effectiveness thresholds (£20,000 and £30,000 per QALY gained). A full exploration of the uncertainty in the conclusions from the modelling will be undertaken. Value of information analyses will also be undertaken to determine those parameters with the greatest influence on the conclusions and to estimate whether future research is likely to represent value for money.

## 11.5 Additional Analysis

Baseline characteristics and follow-up data will be presented using descriptive statistics. A number of exploratory analyses will also be undertaken to support the main analysis:

## 11.5.1 Comparison of the Diagnostic Accuracy of Index Tests Singly and in Combination

The diagnostic accuracy of the index tests (alone and in combination) will be compared initially using Cochran's Q test at the 5% significance level. If significant, then McNemar's test will be used to explore further which test (or combination) is the most accurate compared to the reference standard. Corresponding 95% confidence intervals for the paired differences will also be generated.

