#### 4.2 Study Aim

The purpose of this project is to assess the performance of three rapid tests for fungal infection. The accuracy of these tests will be compared and the optimal test (or combination) identified. The emphasis will be on their ability to rule-out infection so that a test-based protocol for early discontinuation of antifungal therapy can be developed.

This test-based protocol will be modelled for clinical and cost effectiveness, accounting for expected beneficial and adverse outcomes. This modelling, together with a value of information analysis, will inform the design of a future clinical & cost effectiveness RCT.

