#### 11.5.2 Subgroup Analysis

An exploratory sub-analysis of the main diagnostic accuracy analysis will be undertaken to evaluate variation in accuracy measures in the following subgroups: children; patients with end-organ dysfunction, assessed using SOFA & PELOD-2 (when available) score (for adults and children, respectively); whether antifungal treatment had been administered prior to the research blood sample being obtained; patients with infection due to different Candida species; and patients with candidaemia (vs other types of invasive candidiasis, such as peritonitis). This analysis will be expressed using 99% CI.

Doc No: TM09-LB01 Protocol Version 8.0 Final\_27.05.2021 Page 30 of

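### One Cochran's Q over single tests and combinations cannot act as a gate for comparing the three assays; run it on the three single tests alone (minor)

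*Protocol*

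**What the plan says.** Section 11.5.1 of the protocol sets out a two-step comparison. In the first step, "The diagnostic accuracy of the index tests (alone and in combination) will be compared initially using" Cochran's Q; the level is fixed where the tests are to be "compared initially using Cochran's Q test at the 5% significance level". The second step is conditional: "If significant, then McNemar's test will be used to explore further which test (or combination) is the most accurate compared to the reference standard". It adds: "Corresponding 95% confidence intervals for the paired differences will also be generated". The section does not separate single tests from combinations, does not name the accuracy measure to which Q applies, and attaches 5% to Q only.

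Three other places bear on the point:

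- Section 11.2 says that combinations will cover every possible pattern of index test results, so rules nested in one another are in scope.
- Section 11.5 introduces this and the following subsections thus: "A number of exploratory analyses will also be undertaken to support the main analysis".
- Section 4.2 gives the aim that the comparison serves: "The accuracy of these tests will be compared and the optimal test (or combination) identified".

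**The concern.** An omnibus test protects the pairwise tests behind it only if it tends not to reject when the things compared are equal. Here the set compared includes rules that cannot be equal. A rule that is positive when either of two tests is positive can only add positives, so its sensitivity cannot be lower, and its specificity cannot be higher, than those of its components. A rule that needs both positive does the reverse. Unless the assays are fully concordant, Q's null hypothesis is false before any patient is enrolled.

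A significant Q then carries no information on whether the three assays differ from each other, yet it opens the way to their pairwise McNemar tests. At stake is the chance that the report names one assay as more accurate than another that is equally accurate, in the only formal comparison that the protocol gives for the aim in section 4.2.

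**Working it through.** **Inputs from the protocol.** Section 11.1: at least 1188 evaluable patients, 48 with infection, true sensitivity 95%, true specificity 92%. That leaves 1188 − 48 = 1140 without infection. Section 4.3.1: three index tests. Section 11.5.1: Q at 5%.

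**Assumed, because the protocol gives no figure.**

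- All three tests have the sensitivity and specificity above, so every single-test comparison is truly null.
- Latent correlation between tests is 0, 0.5, 0.8 or 0.95. For specificity and sensitivity there is also a case with 0.9 between the two PCR tests and 0.3 otherwise.
- The set entered in Q is either 7 rules (3 single, 3 either-positive pairs, any of three) or 12 (adding 3 both-positive pairs, all three, two of three).
- McNemar's test is run at 5% for each pair.

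**Formulas.** With k rules, column totals C_j, row totals R_i and grand total T of correct classifications, Q = (k−1)[kΣC_j² − T²] / (kT − ΣR_i²), referred to chi-square on k−1 degrees of freedom. McNemar's statistic is (b−c)²/(b+c) on 1 degree of freedom, where b and c are the two discordant counts.

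**Step 1: the stated 5%.** With Q on the three single tests only, scored as correct or incorrect in 1188 patients (4000 simulated trials per correlation), rejection is 4.9-5.2%. The nominal level is reproduced for that comparison.

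**Step 2: why combinations break the gate.** Take independent tests for the arithmetic:

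- Specificity of an either-positive pair: 0.92² = 0.846, so about 0.154 × 1140 = 175 false positives, against 0.08 × 1140 = 91 for a single test.
- Specificity of any of three: 0.92³ = 0.779, so about 0.221 × 1140 = 252 false positives.
- Sensitivity of an either-positive pair: 1 − 0.05² = 0.9975, so about 0.1 missed of 48, against 0.05 × 48 = 2.4 for a single test.

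The built-in gap is very large on specificity. On sensitivity it amounts to about two patients.

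**Step 3: Q over singles and combinations together.**

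| Measure | Q rejects, 7 rules | Q rejects, 12 rules |
|---|---|---|
| Overall accuracy (n=1188) | 100% | 100% |
| Specificity (n=1140) | 100% | 100% |
| Sensitivity (n=48) | 4-54% | 27-97% |

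The first two rows hold at every correlation tried. On sensitivity, rejection falls as the common correlation rises.

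**Step 4: at least one false difference among the three single-test pairs.**

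| Measure | Q with combinations, chi-square McNemar | Same, exact McNemar | Q on three singles only, chi-square McNemar |
|---|---|---|---|
| Overall accuracy | 11.7-12.6% | not run | 4.9-5.2% |
| Specificity | 11.3-13.2% | 8.6-11.6% | 4.5-5.6% |
| Sensitivity | 0.7-11.8% | 0-1.7% | 0.6-3.8% |

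A separate, shorter simulation on overall accuracy gave about 11-14% against about 5-7%. For reference, three independent tests at 5% with no gate give 1 − 0.95³ = 14.3%. On specificity and overall accuracy the pairwise tests therefore behave as if there were no gate. Simulation error is small: with 4000 trials the standard error at 12% is √(0.12 × 0.88 / 4000) = 0.5 percentage points.

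**The case against.** The strongest reply is that nothing promised is broken. The section sits under an exploratory heading, and McNemar's test is there to explore further. The 5% belongs to Q, and Q rejecting a null that is truly false is not a type I error. The primary outcome in section 5.1, the negative predictive value of each test, uses neither Q nor McNemar's test. The statistical analysis plan is not at hand and may list the combinations, name the measure and adjust the pairwise tests. The sentence can even be read as separate Q tests for singles and for combinations. All of this stands and sets the weight of the point. It does not remove it: read literally, the protocol fixes one Q over nested rules, and a missing adjustment is not what is criticised here.

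A reader might infer more than the documents support:

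- *That Q rejects whatever the data.* This holds for specificity and overall accuracy, not for sensitivity, which matters for a study aimed at ruling infection out. With fully concordant tests Q is undefined (0/0), so the case is equally accurate but discordant assays, not identical ones.
- *That a stated 5% error rate is exceeded.* No familywise level is stated for McNemar's test.
- *That 12 rules give 12 × 11 / 2 = 66 unadjusted pairs, with false claims in 23-27% of trials among like-for-like pairs.* The protocol lists no rules, and that figure depends on an assumed list. With exchangeable tests, counting only single and either-positive pairs gives 16-19% on specificity.
- *That the ranking decides which strategy goes forward.* Sections 11.4.1 and 11.4.2 model each test and combination from its estimated accuracy, and section 11.4.2 adds an exploration of uncertainty. No passage drops a strategy on a p-value.
- *That the subgroup rule in section 11.5.2 ("This analysis will be expressed using 99% CI") shows an inconsistency.* Both analyses are exploratory, and the protocol may treat them differently.

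**Conclusion.** The concern holds in a limited form and is minor. As written, the omnibus test does not gate the comparison of the three assays on specificity or overall accuracy: it rejects in about 100% of trials with equally accurate assays, and a false difference between single tests follows in roughly 11-14% of trials instead of about 5%. On sensitivity the effect is uncertain in size, and it is absent with exact McNemar tests.

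This rests on the literal reading of section 11.5.1 as one Q, on the planning figures of section 11.1 applied to all three tests, and on the assumed correlations and rule lists. The 100% rejection does not depend on which of those correlations or lists is used. The 11-14% applies to chi-square McNemar tests at an unadjusted 5%; exact tests on specificity give 8.6-11.6%.

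**What to change.** Reword section 11.5.1 in two parts:

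1. Apply Cochran's Q at 5% to the three single index tests alone, and let that result gate their three pairwise McNemar tests.
2. Compare combinations separately, as a pre-listed set, reported as paired differences with intervals. Any multiplicity adjustment for this set can be left to the statistical analysis plan.

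If separate Q tests were intended all along, one sentence saying so is enough. The change needs no further patients, data or laboratory work. The only statistical price is that the single-test McNemar tests will not be reached when Q on the three assays is not significant, which is what a gate is for.

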#### 5. OUTCOME MEASURES

## **5.1 Primary Outcome Measure**

The primary outcome measure is negative predictive value for each index test. Other diagnostic test accuracy measures will also be reported to support this (comprising sensitivity, specificity, positive predictive value and positive/negative likelihood ratios). The analysis for this primary outcome will be based on an international consensus reference standard for proven invasive fungal disease, applied for Candida infection.

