#### Assumptions:

- (i) In a survey of clinicians, the "minimum acceptable threshold for sensitivity" of a test that would be used to stop empirical antifungals, 90% emerged as an important sensitivity cut-off to influence practice.
- (ii) Based on the above survey, clinicians were asked to select a minimum threshold of NPV to allow discontinuation of antifungals and a value of greater than 98% would satisfy the test performance requirements of all respondents. As the disease prevalence is anticipated to be low, we have set a more stringent criterion of 99% NPV for the sample size calculation.
- (iii) 4% true disease prevalence
- (iv) 92% true test specificity, and 95% true test sensitivity.
- (v) 5% dropout

Among the 1250 participants at least 1188 will provide evaluable data (95%), of whom 48 are expected to have true infection (4%). With up to 4 false negative results with the best index test (or combination), the 95% CI around a point sensitivity estimate of 91.7% would be 80%-97.7%. This indicates the approximate size of the confidence interval envisaged and reflects a degree of precision that is likely to be acceptable to clinicians if the point sensitivity estimate is above 90%.

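### Section 11.5.1 looks for the most accurate test with Cochran's Q and McNemar without naming metric or population: pooled over all participants the ranking follows specificity, and on no reading is NPV compared

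*Protocol*

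**What the plan says.** Section 4.2 sets the aim of comparing the three tests and identifying the best one or best combination, and adds: "The emphasis will be on their ability to rule-out infection so that a test-based protocol for early discontinuation of antifungal therapy can be developed". Section 5.1 states: "The primary outcome measure is negative predictive value for each index test".

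The between-test comparison is in section 11.5.1. The accuracy of the tests, alone and in combination, "will be compared initially using Cochran's Q test at the 5% significance level". If that is significant, "McNemar's test will be used to explore further which test (or combination) is the most accurate compared to the reference standard". The section closes: "Corresponding 95% confidence intervals for the paired differences will also be generated". It does not say which accuracy measure the differences refer to. Nor does it say whether the tests are run in all participants or separately in those with and without infection.

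The planning assumptions in section 11.1 are "4% true disease prevalence" and "92% true test specificity, and 95% true test sensitivity", with 1188 evaluable participants, of whom 48 are infected. The same section sets an NPV criterion of 99% and cites 90% as the sensitivity cut-off that matters to clinicians. Section 11.5 introduces 11.5.1 as one of several exploratory analyses supporting the main analysis.

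**The concern.** A single Q test followed by a search for one *most accurate* test reads most directly as a comparison of right and wrong classifications over the whole cohort. In a cohort that is almost entirely uninfected, most of the disagreements between two tests are disagreements about false positives. A test could then be ranked first for sparing uninfected patients a false positive while missing more true infections, which is the opposite of the rule-out emphasis in section 4.2.

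The second problem does not depend on that reading. McNemar and Cochran's Q need the same participants in every comparison. NPV is a proportion among the participants whom a given test calls negative, so each test has its own denominator. Neither procedure can compare the primary outcome between tests.

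At stake is the evidence for which test or combination should underlie the test-based protocol that section 4.3.1 names as a main objective.

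**Working it through.** **Inputs from section 11.1.** Enrolled 1250; dropout 5%; prevalence 4%; sensitivity 95%; specificity 92%.

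**The plan's own figures.** 1250 × 0.95 = 1187.5, given as 1188. 1187.5 × 0.04 = 47.5, given as 48. The Clopper-Pearson interval for 44/48 is 80.0% to 97.7%, as stated. Uninfected: 1188 − 48 = 1140, and 1140/1188 = 96.0%.

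**What pooled accuracy rewards.** Accuracy = 0.04 × sensitivity + 0.96 × specificity. Since 0.96/0.04 = 24, one point of specificity offsets 24 points of sensitivity. A test with 80% sensitivity matches the 95%/92% test on accuracy at a specificity of 0.92 + 0.15 × 0.04/0.96 = 92.6%.

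**Pooled McNemar.** Let test B have the protocol's 95%/92%, and let test A have an assumed sensitivity of 80% and a specificity between 93% and 96%. A's values are illustrative, because the protocol gives no separate accuracy for each test. Errors are taken as independent given disease status.

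- NPV = 0.96 × spec / [0.96 × spec + 0.04 × (1 − sens)]. For B this is 99.77%, with 48 × 0.05 = 2.4 missed infections expected. A misses 48 × 0.20 = 9.6.
- Expected discordant pairs favouring A: 48 × 0.80 × 0.05 + 1140 × spec of A × 0.08.
- Expected discordant pairs favouring B: 48 × 0.20 × 0.95 + 1140 × (1 − spec of A) × 0.92.
- z = difference between the two counts / square root of their sum.

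| Specificity of A | NPV of A | Accuracy of A (B: 92.1%) | Pairs favouring A | Pairs favouring B | z | A declared better (simulated) |
|---|---|---|---|---|---|---|
| 96% | 99.14% | 95.4% | 89.5 | 51.1 | 3.24 | about 90% |
| 95% | 99.13% | 94.4% | 88.6 | 61.6 | 2.20 | about 58% |
| 94% | 99.12% | 93.4% | 87.6 | 72.0 | 1.23 | about 21% |
| 93% | 99.11% | 92.5% | 86.7 | 82.5 | 0.32 | about 5% |

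The last column is from simulated cohorts with exact McNemar on all 1188 at the two-sided 5% level. Repeat runs gave 88–90%, 55–58%, 20–21% and 4–5%. With A at 96% specificity, B was declared better in 0% of trials, and 92% of the discordant pairs came from uninfected participants.

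**A test that fails the protocol's NPV criterion.** Take A at 75%/97%. Its NPV is 98.94%, below 99%, and it misses 48 × 0.25 = 12 infections. Pairs favouring A: 1.8 + 88.5 = 90.3. Pairs favouring B: 11.4 + 31.5 = 42.9. So z = 47.4/√133.1 = 4.11. The pooled test declares A more accurate in about 99% of trials and B in 0%. With positively correlated errors the figure for A is 99.9%.

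**Insensitivity to missed infections.** With specificity equal at 92%, a fall in sensitivity from 95% to 60% is detected by the pooled test in 23% of trials (39% with correlated errors). The same test restricted to the infected detects it in more than 99% (uncorrected asymptotic McNemar in both cases).

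**Run separately by disease status.** The specificity dominance disappears, but two gaps remain.

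- NPV is still not compared. For A at 80%/96% the expected negatives are 0.96 × 1140 + 9.6 = 1104. For B they are 0.92 × 1140 + 2.4 = 1051.2. The denominators differ in size and in membership.
- There is no rule for conflicting results. An either-positive combination can never be less sensitive, or more specific, than a single test that it contains. When the two do differ, sensitivity and specificity therefore tend to point in opposite directions, and *most accurate* is undefined.

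**The case against.** The strongest reply is that section 11.5.1 does not pool. It speaks of diagnostic accuracy, and sections 5.1, 5.2 and 11.2 spell that out as sensitivity, specificity, predictive values and likelihood ratios. Overall percent correct is never listed. Q and McNemar are sound for sensitivity within the infected and for specificity within the uninfected, and an SAP, not available here, may say exactly that. This stands: a reader might infer that the protocol prescribes a pooled comparison, but the text only makes that the most direct reading.

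A reader might also infer that 11.5.1 alone decides which test is optimal, or that it undermines the primary analysis. The documents support neither. Section 11.5 labels the comparison exploratory. Section 11.2 estimates NPV and sensitivity with 95% confidence intervals for each test, and the same metrics for combinations. Section 11.4 models false negatives explicitly for each strategy. A test with 80% sensitivity would visibly fall short of the 90% cut-off in section 11.1, whatever McNemar showed.

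Two further points stand in part. The size of the effect depends on the assumed specificity gap, as the table shows, and in all four rows A's NPV stays above 99%: A is a poorer rule-out test, not one that fails the NPV criterion. And section 11.2 reports predictive values at a specified prevalence, where NPV is a function of sensitivity and specificity. Paired comparisons of those two therefore inform NPV, although they do not test it.

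What the reply does not remove is that the protocol itself fixes the procedures and the criterion. Neither fits a rule-out aim without a stated metric, population and priority.

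**Conclusion.** The point holds as a should-fix. Without any condition: Cochran's Q and McNemar do not compare NPV, and section 11.5.1 names neither metric nor population, so *most accurate* is not defined. Conditional on the pooled reading: at the planning prevalence the ranking is driven mainly by specificity. Against a 95%/92% test, a test with 80% sensitivity is declared more accurate in about 90% of trials with a 4-point specificity advantage, falling to about 5% with a 1-point advantage. A 75%/97% test, with NPV below 99%, wins in about 99%.

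These figures rest on 48 infected and 1140 uninfected, on assumed accuracies for the comparator test, and, except where correlation is mentioned, on errors independent given disease status. The 96% uninfected is a planning value, not an observed one. The primary per-test NPV estimates are not affected.

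**What to change.** In section 11.5.1:

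- Compare paired sensitivities in reference-positive participants by exact McNemar, with Cochran's Q first where more than two tests are compared. Compare paired specificities likewise in reference-negative participants. State that the confidence intervals are for these differences.
- Add a paired comparison of NPV. Where NPV at a specified prevalence is the planned estimand, use the relative NPV or NPV difference at that prevalence with a bootstrap confidence interval that resamples participants. If sample NPVs are compared, a weighted generalised score test is an alternative.
- State that pooled correct/incorrect agreement is not used to identify the optimal test. State also that the comparison is interpreted on NPV and sensitivity first and specificity second, in line with section 4.2.

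The cost is wording and a little extra analysis on data already collected. The drawback is low power for the sensitivity comparison: with about 48 infected, a difference of 95% versus 80% is detected by exact McNemar in about 49% of trials. The protocol should say so, so that a non-significant difference is not read as equivalence.
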